15.1.4.4. Analysis of covariance

As another supportive analysis for the efficacy endpoints of change from Baseline in SAPS-PD total score at Week 6, missing data at Week 6 will be imputed using the last observation carried forward (LOCF) method, and the data will be analyzed using an ANCOVA model. The response variable for the model will be: change from Baseline in SAPS-PD total score at the Week 6 LOCF endpoint. The ANCOVA model will include treatment as fixed factors and include Baseline score as a covariate.

The proportion of subjects by percent change from baseline at the LOCF Endpoint will be plotted by treatment group.

15.1.4.5. Complete case analysis

The complete case analysis will be performed on the mITT complete case population (see Section 5.5).

The MMRM analysis used in the primary efficacy analysis will be repeated on the above subjects.

15.1.4.6. Analysis on the per protocol population

Sensitivity to the analysis population will be tested by repeating the MMRM analysis used in the primary efficacy analysis on the PP population.

15.1.5. SUBGROUP ANALYSIS OF PRIMARY EFFICACY VARIABLE(S)

For each of the subgroup factors listed in Section 7.5, change from baseline in SAPS-PD total score will be analyzed using the MMRM method. The MMRM model will include fixed effects for treatment, subgroup, visit, baseline SAPS-PD total score, and treatment-by-subgroup, treatment-by-visit, subgroup-by-visit, and treatment-by-subgroup-by-visit interactions.

The estimates obtained from the MMRM models will be presented separately for each subgroup. The p-value for the treatment-by-subgroup interaction at Week 6 will be presented. Its statistical significance will be assessed at the 0.10 level for homogeneity of the treatment effect across the different categories of a subgroup factor. In case a significant interaction effect is detected, estimates by subgroup will be examined to determine the nature of the interaction (qualitative or quantitative).

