8. SELECTION OF SUBJECTS

8.1. Subject Inclusion Criteria

To qualify for participation, subjects must meet all of the following inclusion criteria:

- 1. Subject, caregiver, and/or legally authorized representative understands and is willing to sign informed consent authorizing subject to participate in the study.
- 2. Subject must be willing and able to comply with the study procedures and visit schedules and must be able to follow verbal and written instructions.
- 3. Subject is male or postmenopausal female ≥ 55 years of age.
- 4. Subject meets established diagnostic criteria for Parkinson's disease of at least one year duration, consistent with the UK Brain Bank criteria.
- 5. Subject has psychotic symptoms that began after the diagnosis of PD for at least one month, occurring at least weekly in the month prior to screening (according to subject or caregiver), and severe enough to warrant treatment with antipsychotics.
- 6. Subject has a combined score of at least 6 or an individual score of at least 4 on the Neuropsychiatric Inventory (NPI) Item A (delusions) and/or Item B (hallucinations). This criterion must be met at Visit 1 and Visit 3.
- 7. Subject has a Mini Mental State Examination (MMSE) score > 16 points out of 30.
- 8. Subject has a caregiver (eg, spouse or family member) who will be required to attend all visits and is able to provide study information on various scales such as the NPI.
- 9. Subject is taking antiparkinsonian drugs or deep brain stimulation, with a stable dose/dose regimen and settings for 1 month before screening.
- 10. Female subject must be postmenopausal defined as being amenorrheic for greater than two years with an appropriate clinical profile.
- 11. Male subjects with female partner(s) of childbearing potential must agree to avoid fathering a child and use acceptable methods of birth control from screening until at least 30 days after the last study drug administration.
- 12. Subject is, in the opinion of the Investigator, medically stable based on screening medical history, PE, neurological examination, vital signs, clinical laboratory values (hematology, serum chemistry, urinalysis, lipid panel, coagulation panel, thyroid panel, and serum prolactin).
- 13. Subject has had a stable living arrangement at the time of screening.

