3.4. DETERMINATION OF SAMPLE SIZE

A total of approximately 36 subjects will be randomized in 2:1 ratio to SEP-363856 and placebo, with approximately 24 subjects assigned to SEP-363856 and 12 subjects assigned to placebo. The sample size will provide powers of 59%, 48%, 37%, and 27% to detect treatment effect sizes of 0.8, 0.7, 0.6, and 0.5, respectively, in change from Baseline in SAPS-PD at Week 6 for SEP-363856 versus placebo. It was estimated by using a two independent sample t-test method with 2-sided significant level of 0.05. The sample size was determined for the purposes of exploring the efficacy, safety and tolerability of flexible dosing with SEP-363856 (25, 50, or 75 mg/day) for 6 weeks in male and female subjects with a clinical diagnosis of PDP. A sufficient number of subjects will be enrolled to ensure 36 randomized subjects.

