7.5. EXAMINATION OF SUBGROUPS

Subgroup analyses will be conducted as stated in the respective efficacy and safety analysis sections. It should be noted that the study was not powered to detect treatment differences within subgroups.

The following subgroups will be assessed:

- Sex:
 - Female
 - Male
- Age group (years):
 - >=55 to <65
 - >=65 to <75
 - >=75
- Number of prior hospitalizations for PDP:
 - 0
 - 1
 - 2
 - 3 or more
- Duration of PDP (years):
 - < 5
 - >= 5 to < 10
 - >= 10 to < 20
 - >= 20
- Baseline MMSE (categories for subgroup analysis are different than subgroups presented for the demographic summaries, see Section 10):
 - >24
 - <=24

Document:

\

Author:

Version Number:

Final 1.0

Version Date:

24FEB2020

Template No: CS_TP_BS016 Revision 4
Effective Date: 01Apr2016

Reference: CS_WI_BS005

- Baseline NPI Hallucinations + Delusions (NPI [H+D]) Severity:
 - ≥ 6 to < 12
 - ≥ 12
- Lead-in Status:
 - Lead-in
 - Non Lead-in

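### Eligible subjects with a baseline NPI (H+D) score of 4 or 5 fit no severity subgroup, and four-level subgroup factors have no rule for levels without placebo subjects

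*SAP*

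**What the plan says.** SAP 15.1.5 sets the scope: "For each of the subgroup factors listed in Section 7.5, change from baseline in SAPS-PD total score will be analyzed using the MMRM method". Besides main effects, the baseline score and all two-way interactions, the model contains "treatment-by-subgroup-by-visit interactions". Results are shown by subgroup, and the Week 6 treatment-by-subgroup p-value is judged at 0.10. SAP 15.2.5 repeats the approach for CGI-S.

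SAP 7.5 lists seven factors. Prior hospitalizations for PDP (0, 1, 2, 3 or more) and PDP duration (<5, 5 to <10, 10 to <20, 20 or more years) have four levels each, age has three, and the others have two. One of the two-level factors is "Baseline NPI Hallucinations + Delusions (NPI [H+D]) Severity", split into 6 to <12 and 12 or more. SAP 10 uses the same two bands for the categorical baseline row, and also summarises H+D as a continuous variable.

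Protocol 8.1 (item 6, to be met at Visits 1 and 3) and Protocol 8.3 accept a "combined score of at least 6 or an individual score of at least 4" on delusions and/or hallucinations.

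SAP 3.4 plans about 36 subjects, "with approximately 24 subjects assigned to SEP-363856 and 12 subjects assigned to placebo".

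**The concern.** The entry rule has two routes. The subgroup bands cover only the first, a combined score of at least 6. A subject who enters on one item score of 4, with the other item at 0 or 1, has an H+D of 4 or 5 and belongs to neither band. In a model with the band as a classification factor, a subject without a level contributes nothing. The severity subgroup results would therefore describe fewer subjects than the mITT population, and those left out would be the mildest cases on that scale.

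The second issue is sparseness. A four-level factor in a full three-way model divides about 12 placebo subjects into groups averaging three. If a level contains active subjects but no placebo subjects, its treatment difference cannot be estimated at any visit, and the Week 6 interaction test across all levels cannot be computed as described. The analyst would then have to drop or pool levels after unblinding, with no rule to follow.

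**Working it through.** **The plan's own figure.** SAP 3.4 gives "powers of 59%, 48%, 37%, and 27% to detect treatment effect sizes of 0.8, 0.7, 0.6, and 0.5", using a "two independent sample t-test method with 2-sided significant level of 0.05". With n = 24 and 12, df = 34 and noncentrality d × √(24×12/36) = 2.83d, the noncentral t distribution gives 59.4%, 48.6%, 37.8% and 27.9%. The stated values are reproduced to within one percentage point, so 24 versus 12 is the right base for what follows.

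**NPI (H+D) gap.** SAP 15.2.1.2 defines a domain score as frequency (4-point) times severity (3-point), or zero if the domain is absent. Assuming both scales are coded from 1, the possible scores are 0, 1, 2, 3, 4, 6, 8, 9 and 12. The eligible (delusions, hallucinations) pairs that total less than 6 are:
- (4,0) and (0,4), total 4
- (4,1) and (1,4), total 5

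None has a category. The same section sets H+D to the non-missing domain when the other is missing, so an item score of 4 with a missing partner also falls below 6.

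The documents do not give the share of subjects scoring 4 or 5. For an assumed share f, the expected number is 36f and the chance of at least one is 1 − (1 − f)^36:

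| f (assumed) | Expected of 36 | Chance of at least one |
|---|---|---|
| 5% | 1.8 | 84% |
| 10% | 3.6 | 98% |
| 20% | 7.2 | >99% |

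**Four-level factors.** SAP 15.1.3 uses four visits (Weeks 2, 3, 5 and 6). Cell means: 2 arms × 4 levels × 4 visits = 32. Adding the baseline slope gives 33 fixed effects from about 36 subjects, with on average 3 placebo and 6 active subjects per level.

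- Every level filled (3 versus 6): the design matrix has rank 33, so every contrast is estimable. The standard error of a within-level difference is √(1/6 + 1/3) = 0.71 SD, against √(1/24 + 1/12) = 0.35 SD overall.
- Placebo 9/2/1/0 and active 17/4/2/1: rank 29. The four lost dimensions are the missing placebo means, one per visit, in the level without placebo.

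The harmful event is a level with at least one active and no placebo subject. For a level with share p its probability is (1 − p)^12 × [1 − (1 − p)^24]. The chance that this happens in at least one level was obtained by simulating 12 placebo and 24 active subjects. The last column is the chance that at least two levels contain both arms, so that some interaction can still be estimated. All distributions are assumed.

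| Level shares (%) | Some level: active, no placebo | At least two levels with both arms |
|---|---|---|
| 25/25/25/25 | 12.5% | >99% |
| 40/30/20/10 | 33% | >99% |
| 70/22/7/1 | 50% | 98% |
| 70/18/8/4 | 63% | 97% |
| 80/12/5/3 | 70% | 87% |

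Counting every level without placebo, including levels empty in both arms, would give 94% for 70/22/7/1. That overstates the problem, because a level empty in both arms simply drops out: the 1% level has no subject at all with probability 0.99^36 = 70%.

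For three-level age, the chance of a level without placebo is only about 2% to 5% under the splits tried (equal thirds; 25/45/30).

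**The case against.** These analyses are exploratory (Protocol 15.3.5.5), their p-values are nominal (SAP 7.4), and SAP 7.5 already says the study was not powered for subgroup differences. SAP 19 requires departures from the plan to be described and justified in the report. All of this stands and limits the weight of the point. The power caveat, however, concerns precision. It does not classify a subject with an H+D of 4 or 5, and it does not say what to do with an empty cell. The fallback in SAP 15.1.3 changes only the covariance structure, which cannot repair a missing cell mean. SAP 15.1.4.1 does allow similar discontinuation reasons to be combined when numbers are small, but the subgroup sections contain nothing comparable.

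A reader might infer that some four-level cells are almost sure to be empty and that the interaction p-values cannot be produced. The documents do not support that. They give no distribution of hospitalizations or PDP duration, the model has full rank when levels are filled, and one level without placebo costs that level's estimate and some degrees of freedom, not the whole analysis.

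A reader might also infer that subjects scoring 4 or 5 vanish from the baseline table. They do not. SAP 10 keeps them in the continuous H+D summary and in every other row, and the shortfall in the categorical row would be visible against N. They also stay in the primary MMRM and in the other subgroup factors.

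**Conclusion.** The NPI (H+D) gap is a definite inconsistency between SAP 7.5 and 10 and the entry criteria. Followed literally, the plan leaves eligible subjects scoring 4 or 5 out of the severity subgroup models for SAPS-PD and CGI-S and out of one categorical baseline row. How many are affected is unknown: about 2 to 7 of 36 if the share is 5% to 20%. If nobody with such a score is randomised, nothing is lost.

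The four-level point is a secondary gap in specification. A level's treatment difference may be non-estimable, with a chance of about 13% for equal levels and 33% to 63% for most of the skewed distributions tried, reaching 70% for the most extreme. The interaction among the remaining levels usually stays estimable, though imprecise. These figures assume that all 12 placebo subjects contribute. Missing visits, and the SAP 6.9 rule that treats assessments outside the on-period as missing, would raise them: with 10 placebo subjects the chance of a level without placebo under equal shares rises to about 22%.

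Both points concern exploratory analyses only. The primary analysis is unaffected.

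**What to change.** 1. In SAP 7.5 and in the categorical row of SAP 10, change the lower NPI (H+D) category to <12. Every subject with a non-missing score is then classified. The cost is two small text edits.

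2. For prior hospitalizations and PDP duration, either use two levels (0 versus 1 or more; <5 versus 5 or more years), or state before unblinding that a level without subjects in both arms is pooled with the adjacent level. Two levels cut the fixed effects from 33 to 2 × 2 × 4 + 1 = 17 and raise the average placebo count per level from 3 to 6. The chance of a level without placebo, p^12 + (1 − p)^12, becomes 0.05% for a 50/50 split, 0.2% for 60/40 and 6.9% for 80/20. Because the last figure is not negligible, the pooling rule is worth having for the four-level version, and with two levels a sentence should say that the model is not fitted if a level lacks one arm. The two cut-points are suggestions; the documents give no basis for preferring them. The cost is a coarser subgroup description.

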15.1.6. ANALYSIS OF PRIMARY EFFICACY VARIABLE FOR OPEN-LABEL PERIOD(s)

The observed values of the primary efficacy measures at the OL baseline, and at each scheduled post-baseline open-label extension visit, will be summarized descriptively. Changes from open-label baseline in these measures will be summarized at each scheduled post-baseline open-label extension visit, based on both the DB and the OL baseline... .

15.2. SECONDARY EFFICACY

The analyses of the secondary efficacy variables will be performed on the mITT population.

Document:	\
Author:	Version Number: Version Date:
Template No: CS_TP_BS016 Revision 4 Effective Date: 01Apr2016	Final 1.0 24FEB2020 Reference: CS_WI_BS005

15.2.1. SECONDARY EFFICACY VARIABLES & DERIVATIONS

15.2.1.1. Change from baseline in CGI-S score at Week 6

The CGI-S is a clinician-rated assessment of the subject's current illness state on a 7-point scale, where a higher score is associated with a greater illness severity. The CGI-S score takes one of the following values: 1 (normal, not at all ill), 2 (borderline mentally ill), 3 (mildly ill), 4 (moderately ill), 5 (markedly ill), 6 (severely ill), 7 (among the most extremely ill patients). Only subjects on-period data will be taken into account in this analysis (see Section 6.9).

15.2.1.2. Change from baseline in NPI score and NPI (H+D) score at Week 6

The NPI (Cummings-1994) is a 12-item behavior rating scale composed of a structured interview of the caregiver, which assess psychiatric disturbance. The 12 sub-domains are the following:

- o Delusions
- o Hallucinations
- o Agitation\Aggression
- o Depression\Depression
- o Anxiety
- o Elation\Euphoria
- o Apathy\Indifference
- o Disinhibition
- o Irritability\Lability
- o Aberrant Motor behavior
- o Sleep and Nighttime behavior disorders
- o Appetite and eating changes

For each sub-domain, a gating question is asked:

- If the responses to these questions indicate that the patient has problems with a particular subdomain of behavior, the caregiver is only then asked all the questions about that domain, rating the frequency of the symptoms on a 4-point scale and their severity on a 3-point scale (Cummings-1997). The sub-domain score is the product of the frequency score multiplied by the severity score for that behavioral domain, it will be calculated by statistical programming, the results of the eCRF will not be used. In case of any missing data for frequency or severity then the sub-domain score will be set to missing.
- If the responses to these questions indicate that the patient does not have problems with that particular subdomain of behavior, that sub-domain score will be set to zero.

For each sub-domain, a measure of the level of caregiver distress is also given but is not included in the NPI score and not used in any statistical analysis.

A NPI score is obtained by summing all the sub-domain scores. Only subjects on-period data will be taken into account in this analysis (see Section 6.9).

For the combined score NPI (H+D) = NPI hallucinations + NPI delusions, if either domain is missing, the combined score will be set to the non-missing domain score. If both domain scores are missing, then

Document:

\

Author:

Version Number:
Version Date:Final 1.0
24FEB2020Template No: CS_TP_BS016 Revision 4
Effective Date: 01Apr2016

Reference: CS_WI_BS005

the combined score will be set to missing.

15.2.1.3. Change from baseline in MMSE score at Week 6

The MMSE for Cognition (Folstein-1975) is a brief instrument, used to assess cognitive function, consisting of 11 tests including orientation, memory (recent and immediate), concentration, language, and praxis. Scores range from 0 to 30, with lower scores indicating greater cognitive impairment. The total score will be calculated by statistical programming, the results of the eCRF will not be used. Only subjects on-period data will be taken into account in this analysis (see Section 6.9).

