15.3.11. Treatment of Missing Data

For rating scales with more than one item, such as SAPS-PD, if any item score contributing to the total/subscale score is missing, then the total/subscale score will be set to missing.

For the MMRM models, no imputation for missing data will be applied unless otherwise specified.

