15.2.2. MISSING DATA METHODS FOR SECONDARY EFFICACY VARIABLE(S)

For rating scales with more than one item, if any item score contributing to the total score or individual domain score is missing, then the total score or individual domain score will be set to missing. The change from baseline scores will also be set to missing accordingly.

Document:

\

Author:

Version Number:
Version Date:

Final 1.0
24FEB2020

Template No: CS_TP_BS016 Revision 4
Effective Date: 01Apr2016

Reference: CS_WI_BS005

The MMRM analysis of the continuous secondary efficacy variables will be based on observed data (with early termination data mapped as described in Section 6.4). Missing data will not be imputed. SAPS-PD responder calculation will be based on the SAPS-PD total score at the Week 6 LOCF endpoint.

The ANCOVA analyses of the continuous secondary efficacy variables will utilize the change from baseline at the Week 6 LOCF endpoint, as a sensitivity analysis. Refer to section 6.3 for further details on LOCF imputation.

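### NPI (H+D) counts a missing domain as zero, and its baseline categories leave out eligible totals of 4 and 5

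*SAP*

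**What the plan says.** SAP 15.2.1.2 gives the score as "NPI (H+D) = NPI hallucinations + NPI delusions". For each domain, "The sub-domain score is the product of the frequency score multiplied by the severity score for that behavioral domain". A domain is zero when the gating question shows no problem. When the gate does show a problem, frequency and severity are rated, and "In case of any missing data for frequency or severity then the sub-domain score will be set to missing". For the combined score the SAP then says that "if either domain is missing, the combined score will be set to the non-missing domain score"; it is missing only when both domains are.

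The general rules differ. Protocol 15.3.11 says of multi-item scales that "if any item score contributing to the total/subscale score is missing, then the total/subscale score will be set to missing". SAP 15.2.2, for the secondary variables, makes a total or domain score missing "if any item score contributing to the total score or individual domain score is missing", and adds that the MMRM uses observed data without imputation. SAP 7.3 repeats the rule but allows for exceptions specified elsewhere. SAP 3.7 declares no change from the protocol analysis.

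SAP 7.5 lists "Baseline NPI Hallucinations + Delusions (NPI [H+D]) Severity" as a subgroup factor with two levels, 6 to below 12 and 12 or more. SAP 10 uses the same two levels in the baseline table. Protocol 8.1, inclusion criterion 6, admits a "combined score of at least 6 or an individual score of at least 4" on the delusions and hallucinations items; Protocol 8.3 repeats this for randomization.

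**The concern.** Replacing a two-part sum by one part amounts to imputing zero for the other. Zero has a specific meaning in this scale: symptom absent. When the lost domain was above zero at baseline and goes missing later, the subject appears to improve. When it is lost at baseline, the subject appears to worsen.

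NPI (H+D) is the NPI measure closest to what SAPS-PD measures. SAP 15.2.3.2 gives it the same analysis as the NPI total and plans to explore its relationship with SAPS-PD, so a false change would enter both. With 24 and 12 subjects planned, single records matter.

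The category gap is a second defect in the same variable and needs no missing data. Subjects with milder symptoms who are properly enrolled have no place in the severity subgroup analysis or in the categorical rows of the baseline table.

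**Working it through.** The plan gives no figure of its own on this point. Its power figures concern SAPS-PD and do not enter here.

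**Inputs**
- Combination rule and domain scoring: SAP 15.2.1.2.
- Change = visit value minus baseline: SAP 6.10. Lower is better.
- Planned arm sizes: 24 SEP-363856, 12 placebo (SAP 3.4).
- Assumption: the documents describe frequency as a 4-point and severity as a 3-point scale without giving the codes. With codes 1-4 and 1-3, the possible domain scores are 0, 1, 2, 3, 4, 6, 8, 9 and 12, so H+D runs from 0 to 24.

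**1. The rule applied to single subjects** (H = hallucinations, D = delusions)

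| Baseline H, D (sum) | Week 6 H, D | Scored at Week 6 | Change under the SAP rule |
|---|---|---|---|
| 8, 6 (14) | 8, missing | 8 | 8 - 14 = -6 |
| 8, 4 (12) | missing, 4 | 4 | 4 - 12 = -8 |
| 12, 12 (24) | 12, missing | 12 | 12 - 24 = -12 |
| 6, 4 (10) | 9, missing | 9 | 9 - 10 = -1 |
| 8, 0 (8) | 8, missing | 8 | 8 - 8 = 0 |
| 8, missing (scored 8) | 8, 4 | 12 | 12 - 8 = +4 |

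The first three rows show improvement with no change in the observed domain. In the fourth, the observed domain worsens by 3 and the score still falls. In the fifth, a new symptom is hidden. The last is false worsening from a gap at baseline.

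**2. Effect on an arm mean.** If k subjects in an arm of n have one domain missing at Week 6 and its true score is m, the raw mean change shifts by -k × m / n.
- m = 6, k = 1: -6/24 = -0.25 (SEP-363856); -6/12 = -0.50 (placebo).
- m = 6, k = 2, placebo: -12/12 = -1.00.
- m from 2 to 12, k = 1: -0.08 to -0.50 with n = 24; -0.17 to -1.00 with n = 12.

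The direction of the bias in the treatment difference depends on the arm in which the gap falls.

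**3. Where the false value goes.** In the double-blind period the NPI is taken at Visits 3, 5 and 7 (Protocol Table 2), so a false post-baseline value is one of at most two in the MMRM. Because a partial score counts as non-missing, the LOCF rule in SAP 6.3 would not replace it and could carry it forward. At baseline it would also block the fallback in SAP 6.2 to an earlier complete pre-dose value, although the NPI is also taken at Visit 1.

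**4. Category gap.** A total below 6 is eligible only if one domain is at least 4. On the score values above, that leaves 4 + 0 = 4 and 4 + 1 = 5. Neither falls in 6 to below 12, nor in 12 or more.

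**The case against.** The best defence is that SAP 7.3 allows exceptions and SAP 15.2.1.2 states one explicitly, so a programmer faces no ambiguity; and NPI (H+D) is not a protocol endpoint. That defence is incomplete. SAP 15.2.2 and the protocol's sentence on item scores carry no such allowance, SAP 10 lists H+D among the NPI subscale scores, and no reason for the exception is given. Even a consistent exception would still score a reported symptom as absent.

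Several other points stand as limits:
- The trigger is narrow. A missed visit loses both domains and is handled correctly, and the NPI is a structured interview conducted by a rater. A gap at baseline should be rarer, since these two items are checked for entry, though one domain of 4 can qualify alone.
- False improvement requires that the lost domain was above zero at baseline.
- The shifts are raw means on planned numbers, not adjusted MMRM estimates.
- Setting the score to missing has its own weakness. The gaps arise after a positive gate, so symptomatic observations are the ones lost, and missing at random may not fully hold.
- Subjects with totals of 4 or 5 stay in the main analyses and in the continuous baseline summary, and SAP 7.5 itself says the subgroups were not powered.

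**Conclusion.** The concern holds. Followed as written, the rule gives an understated NPI (H+D) whenever a single domain is missing with a true score above zero, and on the route the SAP describes that score is at least 1 under the assumed coding. The error per record equals the missing domain's true score, at most 12. In an arm mean, one record is worth up to -0.50 with 24 subjects or -1.00 with 12. How often this will happen cannot be told from the documents.

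The category gap is certain from the text for a total of 4; the total of 5 also rests on the assumed coding.

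The consequence is confined to one secondary variable added in the SAP and reported with nominal p-values. The SAPS-PD primary score and the 12-item NPI total are derived correctly. The change should be made, but it does not put the primary conclusion at risk.

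**What to change.** - In SAP 15.2.1.2, replace the combination rule with: if either domain score is missing, NPI (H+D) is set to missing. The MMRM then treats it as it does any other missing value, LOCF can act on it, and the SAP agrees with its own 15.2.2 and with Protocol 15.3.11.
- Report the number of partly missing NPI (H+D) records by arm and visit. If there are any, add a sensitivity analysis over plausible values of the missing domain, because missing at random is open to doubt here.
- In SAP 7.5 and 10, change the lower category to below 12 (or 4 to below 12).
- If the sponsor keeps the exception, it should justify it, list it under SAP 3.7 and add a sensitivity analysis with the score set to missing.

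The cost is a few lines of SAP wording and, at most, a few values that become missing.
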